#### 4.8.6 Vital Signs, Physical Findings and Other Observations Related to Safety

For this study, vital signs include systolic and diastolic blood pressure, heart rate, respiratory rate, body temperature, and weight. Each vital sign parameter will be analyzed as continuous variable in the way described in Section 4.2. For by-visit summaries, the last non-missing assessment (including repeat assessments, if any) recorded at each visit will be used for summarization.

Abnormalities identified during the physical examination will be summarized across infusion schedule and overall by visit. Clinical significance of the abnormalities will be evaluated and presented. In addition, a shift table will be produced to summarize the change from baseline in categorical data. The three categories for both the physical examination are as follows: normal, abnormal-not clinically significant, and abnormal-clinically significant. A by-subject listing will also be provided for physical examinations.

Blood samples for the preparation of serum will be collected from all subjects at screening prior to each infusion of GC5107 and at the Follow-up visit to determine the trough levels of total IgG.

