	
(AEs) that occur during or within 1 hour, 24 hours, and 72 hours following an infusion of investigational product (including AEs that were determined to be unrelated to the product).
 
2) Secondary Safety Endpoints
 
 
• The overall incidence of all AEs that occur during or within 1 hour, 24 hours ,and 72 hours following an infusion of investigational product.
 
• The frequency of all AEs that occur during the study regardless of the investigator’s assessment of their relationship to investigational product.
 
• The frequency of suspected adverse reactions as defined by all AEs either classified by investigator or sponsor as at least possibly related to GC5107.
 
• Changes in vital signs, physical examinations, and laboratory test results.
 
• The number and proportion of GC5107 infusions for which the infusion rate was decreased due to AEs.
 
• The proportion of AEs considered by the investigator to be investigational product related.
 
• Viral safety (freedom from transmission of blood-borne viral diseases): the human immunodeficiency virus (HIV) 1&2, hepatitis A virus (HAV), hepatitis B virus (HBV), hepatitis C virus (HCV), and parvovirus B19.
 

PHARMACOKINETIC ENDPOINTS
	
1) Primary PK Endpoints
 
 
• PK parameters of total IgG (assessed in PK population).
 
• Trough serum total IgG levels before each infusion of GC5107 in all subjects and the interval between infusions will be recorded.
 
 
2) Secondary PK Endpoints
 
 
• PK parameters of IgG subclasses (assessed in PK population)
 
• Trough serum level of IgG subclasses and specific IgG antibodies before Infusion 1, 5, 9, 13 (for 28-day infusion subject) or Infusion 1, 5, 11, 17 (for 21-day infusion subject)
 
 
 
○ anti-Hemophilus influenza type b
 

	

○ anti-Streptococcus pneumoniae serotypes

○ anti-Tetanus toxoid

○ anti-Cytomegalovirus (CMV)

● Number and proportion of subjects who failed to meet the target IgG trough level (500 mg/dL) at any time point equal to or subsequent to 5th infusion (estimated 5 half-lives).

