## REVISION HISTORY

Version No.	Effective Date	Summary of Change(s)
1.0	17 Jun 16	New document
2.0	19 Oct 16	
 
• Section 4.3.1 (Disposition of Subjects), added more details to the summary of subject withdrawn from study.
 
• Section 4.5 (Demographic and Other Baseline Characteristics ....), deleted the analysis of “Prior only” medication.
 
• Section 4.7.1.3 (Handling of Dropouts or Missing Data), deleted the summary of missing data for the primary endpoint.
 
• Section 4.9 (Pharmacokinetic Endpoint), QCD scientist added details for PK analysis. QCD scientist co-author the SAP
 
• MedDRA dictionary version changed from 18.1 to 19.1
 
• Correct “first dose” to “first infusion”, “last dose” to last infusion.
 

3.0	06 Aug 19	
 
• According to Protocol v2.0 Amendment 1, added safety visits (72 hours after the end of the first and second infusion). Second Follow-up after last infusion is deleted.
 
• According to Protocol v2.0 Amendment 2, Time windows for PK sampling points are clarified in section 4.9, in addition to Pharmacokinetic Parameters of Total IgG and Serum Levels of IgG Subclasses.
 
• According to according Protocol v 2.0 Amendment 3, the number of pediatric subjects is changed from 12 to 8. The wording of ‘evaluable’ is deleted in the definition of analysis population.
 
• According the FDA’s review feedback, added ITT2 population, and geographic region.
 
• Added imputation method to the algorithm of duration of AEs during infusion, and the duration of hospitalization.
 
• Added the definition of follow-up time for each subject.
 
• Added clarification for Aes that occur during or within (a) 1 hour, (b) 24 hours, and (c) 72 hours following an infusion; clarification for time of onset of Aes occurs during infusion, and AE duration;
 

		
clarification for AE leading to discontinuation, dose interruption, and rate change.
 
 
• Deleted summary of abnormal vital sign.
 
• Clarified the PK endpoint and corresponding analysis population.
 
• In Section 4.11, clarified any analysis that is deviated from protocol specified statistics analysis.
 
• To clarify the meaning and to be consistent through the whole texts, some words are revised or added.
 

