## 2.4 Secondary Safety Endpoints/Variables

- The overall incidence of all AEs that occur during or within 1 hour, 24 hours, and 72 hours following an infusion of investigational product.
- The frequency of all AEs that occur during the study regardless of the investigator's assessment of their relationship to investigational product.
- The frequency of suspected adverse reactions as defined by all AEs either classified by investigator or sponsor as at least possibly related to GC5107.
- Changes in vital signs, physical examination, and laboratory results.
- The number and proportion of GC5107 infusions for which the infusion rate was decreased due to AEs.
- The proportion of AEs considered by the investigator to be investigational product related.
- Viral safety (freedom from transmission of blood borne viral diseases): HIV-1&2, HAV, HBV, HCV, and parvovirus B19.

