### 4.2 General Presentation Considerations

‘Baseline’ is defined as the last available pre-treatment assessment, unless specified in later section. ‘End of Study’ is defined as the last available post-treatment assessment. ‘Treatment Day’ will be calculated relative to the date of the first infusion of GC5107, i.e. Treatment Day = Assessment Date - First Infusion Date + 1 (if on or after day of first infusion); or Treatment Day = Assessment Date - First Infusion Date (if before day of first infusion).

Continuous data will be summarized in terms of the mean, standard deviation (SD), median, minimum, maximum and number of observations, unless otherwise stated. Continuous data that are expected to be skewed will be presented in terms of the maximum, 75% quantile, median, 25% quantile, minimum and number of observations. The minimum and maximum will be reported to the same number of decimal places as the raw data recorded in the database. The mean, median, lower quartile and upper quartile will be reported to one more decimal place than the raw data recorded in the database. The SD will be reported to two more decimal places than the raw data recorded in the database. In general, the maximum number of decimal places reported shall be four for any summary statistic.

Categorical data will be summarized in terms of the number of subjects providing data at the relevant time point (n), frequency counts and percentages. . Any planned collapsing of categories will be detailed in the SAP text and the data displays.

Percentages will be presented to one decimal place. Percentages will not be presented for zero counts. Percentages will be calculated using N as the denominator unless otherwise indicated. If sample sizes are small, the data displays will show the percentages, but any textual report will describe frequencies only.

Changes from baseline in categorical data will be summarized using shift tables where appropriate. For continuous variables, actual values and changes from baseline will be summarized using descriptive statistics across infusion schedule and overall by visit.

P-values greater than or equal to 0.001, in general, will be presented to three decimal places. P-values less than 0.001 will be presented as “<0.001”.

Confidence intervals will be presented to one more decimal place than the raw data.

All report outputs will be produced using SAS® version 9.3 or a later version in a secure and validated environment.

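### SAP 4.8.6 summarizes only the last vital-sign reading of each visit, so if several are taken, transient infusion changes and abnormal readings later repeated leave the by-visit safety summary

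*SAP*

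**What the plan says.** Both documents make changes in vital signs a secondary safety endpoint: "Changes in vital signs, physical examinations, and laboratory test results" in the protocol synopsis and "Changes in vital signs, physical examination, and laboratory results" in SAP 2.4.

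SAP 4.8.6 sets the analysis: "Each vital sign parameter will be analyzed as continuous variable in the way described in Section 4.2". It then adds that, for by-visit summaries, "the last non-missing assessment (including repeat assessments, if any) recorded at each visit will be used for summarization".

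SAP 4.2 supplies the rest. For continuous variables, "actual values and changes from baseline will be summarized using descriptive statistics across infusion schedule and overall by visit". Baseline "is defined as the last available pre-treatment assessment, unless specified in later section", and 4.8.6 specifies no other baseline.

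For physical examinations, 4.8.6 also provides a summary of abnormalities, a shift table and a listing: "A by-subject listing will also be provided for physical examinations". The text available gives no such items for vital signs.

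**The concern.** GC5107 is infused at rates that rise in steps, so part of the purpose of measuring vital signs is to see what happens over the course of an infusion. A rule that keeps one value per visit, and prefers a repeat to the reading that prompted it, can leave a fall in blood pressure, a fast heart rate or a fever out of the table if it has passed by the last reading.

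Measured vital signs are also a check on safety that does not depend on anyone judging an event to be an AE. If the summary omits transient excursions, a report could describe vital signs as unchanged although the recorded data contain changes that the table was not built to show.

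**Working it through.** The plan gives no figure on this point to reproduce. The check sets the provisions side by side, with some arithmetic on the infusion course and the reach of the rule.

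**Inputs**
- Reading used, one per visit and the last non-missing: SAP 4.8.6.
- Baseline *b*, the last assessment before treatment: SAP 4.2.
- Summary level, by visit: SAP 4.2.
- Infusion rates and dose range (300 to 900 mg/kg): protocol synopsis.
- Infusions per subject, 13 (28-day) or 17 (21-day): SAP Section 3, Table 1.
- Readings per infusion visit, *k*: not in the text available. **Assumption:** *k* is 2 or more; at *k* = 1 the rule removes nothing.

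**1. What the table can contain.** Let the readings at one infusion visit be v0 (pre-infusion), v1, ..., vL, where vL is the last. The by-visit table receives vL and vL − *b*. The change over that infusion is vj − v0 for the later readings j. Neither v0 nor any vj before vL enters the table.
- If an excursion at vj has returned to v0 by vL, the table shows v0 − *b*, the same entry as if there had been no excursion.
- If vj is abnormal and is repeated, the repeat or a later reading is used. This follows from the words of the rule, whatever the number of readings.
- At infusion 1, *b* may be that day's pre-infusion reading, so the change to the last reading can be shown. From infusion 2 on, *b* belongs to an earlier date, and even vL − v0 is not available.

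**2. How long a course one reading stands for.** Taking the scheduled rates without slowing:
- First infusion, delivered by 90 minutes: 1 × 30 + 2 × 30 + 4 × 30 = 210 mg/kg. The remainder runs at 8 mg/kg/min: (300 − 210)/8 = 11 minutes to (900 − 210)/8 = 86 minutes. Total: about 101 to 176 minutes.
- Later infusions, delivered by 30 minutes: 2 × 15 + 4 × 15 = 90 mg/kg. The remainder: (300 − 90)/8 = 26 minutes to (900 − 90)/8 = 101 minutes. Total: about 56 to 131 minutes.

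**3. Reach.** For 42 completers: 42 × 13 = 546 to 42 × 17 = 714 planned infusions. This counts visits to which the rule applies, not visits at which an abnormal value is lost.

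**4. Whether another summary restores the values.** In the text available, vital signs have no table by time point, no extreme values, no abnormality table and no listing. The revision history for SAP version 3.0 records "Deleted summary of abnormal vital sign". That entry is not an error; it only supports the reading that the current plan has no abnormal-value summary. The exploratory fever endpoint in SAP 4.7.4 is built from treatment-emergent AEs coded as pyrexia, not from measured temperatures.

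**The case against.** The strongest reply has four parts.

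- **Several readings per visit are not established.** Protocol 8.1.1 and the evaluation schedules are not in the text available, and the rule mentions repeats only if there are any. It may be meant as a tie-break for occasional repeats. This stands as a limit: the consequence for infusion-time changes depends on *k* being at least 2. The consequence for a repeated abnormal reading needs only the repeat.
- **Text is missing around SAP 4.8.6.** A vital-sign listing or time-point table there cannot be ruled out. This also stands, although a listing alone would not repair the summary of the endpoint.
- **Infusion safety is assessed mainly elsewhere.** The primary safety endpoint counts AEs during and within 1, 24 and 72 hours after an infusion, related or not, and infusions slowed because of AEs are a separate endpoint. This limits the practical effect, but those analyses see an excursion only if it was recorded as an AE.
- **The endpoint is descriptive and does not name a within-infusion comparison.** That is true, and it limits the weight of the point. It does not explain why recorded readings should be left out of the summary.

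A reader might infer three stronger things that the documents do not support:
- *That the last reading is the one furthest from the peak rate.* The scheduled rates only rise, and by the arithmetic above the final 11 to 86 minutes (first infusion) or 26 to 101 minutes (later ones) run at the maximum. The timing of the last reading is not given.
- *That the selection acts only towards normal.* A change that emerges late or persists to the last reading is kept.
- *That the share of readings not used, (k − 1)/k, measures the harm.* It counts normal and pre-infusion readings too, and says nothing about how many abnormal values are lost.

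**Conclusion.** The point holds in a limited form. As written, SAP 4.8.6 with SAP 4.2 cannot show transient vital-sign changes at an infusion visit. It replaces an abnormal reading by any later one at that visit. From the second infusion on, it offers no comparison with the reading before that infusion.

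This rests on the assumption that more than one reading is taken at infusion visits, and on the text available containing all the vital-sign summaries. The number of abnormal values affected cannot be estimated from the documents. The readings remain in the database, and the primary efficacy and primary safety tests do not change. The plan should be amended because the loss is avoidable at little cost, but no main conclusion of the trial depends on it.

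**What to change.** In SAP 4.8.6, replace the single-value rule for infusion visits with three summaries for each parameter:

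1. the pre-infusion value at that visit;
2. the largest rise and the largest fall from that value among the later readings of the visit, keeping original readings even when they were repeated;
3. the last value of the visit, as now.

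At all visits, including those without an infusion, keep the original abnormal reading alongside any repeat, in the summary or in a by-subject listing. The SAP should also state how many readings protocol 8.1.1 calls for. If it is one per visit, only the provision on repeats is needed.

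The cost is SAP wording and a few extra table rows from data already recorded. Maxima and minima are noisier than last values, because a single stray reading can determine them; showing them beside the pre-infusion and last values lets the reader allow for that. No visit, measurement or treatment rule changes.

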#### 4.9.1.2 IgG Subclasses/Specific Antibodies – Trough Levels (pre-infusion of GC5107)

28-day Infusion Subjects: IgG subclasses, specific antibodies trough levels - at Infusions 1, 5, 9, and 13.

21-day Infusion Subjects: IgG subclasses, specific antibodies trough levels - at Infusions 1, 5, 11, and 17.

#### 4.9.1.3 Pharmacokinetic Parameters of Total IgG and Serum Levels of IgG Subclasses

Blood samples will be collected from at least 20 subjects before and after the 5th infusion of investigational product. The samples will be used to measure the serum concentrations of total IgG and IgG subclasses. The PKs of total IgG will be determined.

The following PK parameters for total IgG will be determined using uncorrected values and baseline-corrected values when IgG values prior to immunoglobulin therapy are available.

- Plasma concentration-time curve
- Half life will be calculated as  $\ln_2/\lambda_z$
- Area under the curve ( $AUC_{0-t}$ ,  $AUC_{0-24h}$  and  $AUC_{0-inf}$ ) and the area under the concentration times time versus time curve (AUMC) will be calculated by linear–log trapezoidal method (linear method will be employed for all incremental trapezoids arising from increasing concentrations and the logarithmic method will be used for those arising from decreasing concentrations)
- Volume of distribution ( $V_d$ ) will be estimated as  $V_z$  and  $V_{ss}$ . No values will be specifically generated or reported for  $V_d$ . Maximum concentration ( $C_{max}$ ) will be obtained directly from the concentration-time data
- Minimum (trough) concentration ( $C_{min}$ ) will be obtained directly from the concentration-time data at pre-dose
- Time of maximum concentration ( $T_{max}$ )
- Clearance (CL) will be calculated as  $dose/AUC_{0-inf}$
- IR (incremental recovery) will be estimated as  $(C_{max} - C_{min})/dose$  per body weight
- $IR_{30min}$  (incremental recovery) will be estimated as  $(C_{30min} - C_{min})/dose$  per body weight, where  $C_{30min}$  is the observed Total IgG concentration at 30min post-infusion
- $\lambda_z$  will be estimated at terminal phase by linear regression after log-transformation of the concentrations
  - Only those data points that are judged to describe the terminal log-linear decline will be used in the regression.

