
DOSAGE REGIMEN
	
 
• All subjects will receive intravenous infusions of the investigational product at the same dose and interval as used for their previous IGIV maintenance therapy
 
• Dose of 300 – 900 mg/kg (of body weight) every 21 or 28 days (<math>\pm 4</math> days) for 12 months
 

TARGET TROUGH LEVEL
	
<math>\geq 500</math> mg/dL (5 g/L)

STUDY PERIOD
	
Approximately 14 months / each subject:
 
 
• Screening: up to 28 days
 
• Treatment (investigational product infusions) period: 12 months
 
• Follow-up period: 3 or 4 weeks
 

INCLUSION CRITERIA
	
 
1. Subject has a confirmed clinical diagnosis of a PHID disease as defined by International Union of Immunological Societies (IUIS) and requires treatment with IGIV, and has documented agammaglobulinemia or hypogammaglobulinemia.
 
2. Male or female, aged 2 to 70 years.
 
3. The subject has received 300-900 mg/kg of IGIV therapy at 21(<math>\pm 4</math> days) or 28(<math>\pm 4</math> days)day intervals for at least 3 infusion prior to this study.
 
4. At least 2 documented IgG trough levels of <math>\geq 500</math> mg/dL are obtained at two infusion cycles
 

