ANALYTICAL PLAN / STATISTICAL METHOD	
Efficacy data will be evaluated by comparing the number of acute serious bacterial infections per subject per year according to the FDA guideline of an upper one-sided 99% confidence limit < 1.0 per subject per year. The primary safety endpoint will be analyzed with the objective of demonstrating that the percentage of infusions with one or more infusion-related AE is less than 40%. Pharmacokinetic parameters (clearance, mean residence time, volume of distribution, and terminal half-life) will be estimated by fitting noncompartmental analysis individually to the data for each subject in the PK population, except for the AUC which will be determined using a (log-) trapezoidal rule as the area above the previous trough level. Pharmacokinetic parameters will be derived from serum IgG levels and presented descriptively. Trough levels of IgG subclasses will be summarized relative to dosing interval. All other data will be reported descriptively.

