### Investigators and Study Centers

---

[REDACTED]

[REDACTED]

[REDACTED]

A sufficient number of study sites to enroll up to 50 subjects to obtain at least 26 adult subjects, at least 8 adolescent subjects and at least 8 child subjects will be recruited. Subjects who withdraw (or are withdrawn) will not be replaced.

Randomization and Stratification

Not applicable.

Blinding

Not applicable.

Treatment Regimens

All subjects will receive intravenous infusions of investigational product at the same dose and interval as used for their previous IGIV maintenance therapy. GC5107 will be administered at a dose of 300 - 900 mg per kg (of body weight) every 21 or 28 days ( $\pm 4$  days) for a period of 12 months.

Visit Schedule

The Table 1 below summarizes the timeline for the study. For detailed visit schedule, please refer to the study protocol for GC5107B\_P3 (Section 5.8).

Table 1: Study Timeline

Procedure 28 day regimen (21 day regimen in parentheses)	Time	
Screening*	Day -28 to Day -1 (Day -21 to Day -1)	Up to 28 days prior to the first infusion
Infusion 1	Week 0, D1 Baseline	12 months of infusions
Infusion 2-4 (Infusion 2-4)	Week 4 – 12 (Week 3-9)	
PK Assessment Infusion 5 (Infusion 5)	Week 16 (Week 12)	
Infusion 6 – 13 (Infusion 6 - 17)	Week 20 – 48 (Week 15- 48)	

Follow-up: 4 weeks after last infusion (3 weeks after last infusion)	Week 52 (Week 51)	3 or 4 weeks after the last investigational product infusion
--	----------------------	--

Note: The screening procedures can occur only after a potential subject has signed the ICF. Results of screening must be obtained before the first study infusion.

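### SAP 4.9.1.3 computes clearance as dose/AUC0-inf from the infusion-5 profile, so IgG carried over from earlier infusions is counted and CL comes out too low

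*SAP*

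**What the plan says.** SAP 4.9.1.3 derives the PK parameters of total IgG from samples taken before and after infusion 5 (SAP section 3, Table 1: "PK Assessment Infusion 5 (Infusion 5"). For clearance it gives "Clearance (CL) will be calculated as $dose/AUC_{0-inf". It lists AUC0-t, AUC0-24h and AUC0-inf, but no AUC over the dosing interval. Values are reported uncorrected and, as the only correction, as "baseline-corrected values when IgG values prior to immunoglobulin therapy are available".

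The dosing history is set out elsewhere:
- Protocol synopsis, inclusion criterion 3, requires IGIV at 21- or 28-day "intervals for at least 3 infusion prior to this study".
- Under Treatment Regimens, SAP section 3 states: "All subjects will receive intravenous infusions of investigational product at the same dose and interval as used for their previous IGIV maintenance therapy". The study product is given "every 21 or 28 days ( $\pm 4$ days) for a period of 12 months".
- The synopsis describes infusion 5 in the secondary PK endpoint as "at any time point equal to or subsequent to 5th infusion (estimated 5 half-lives".

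The synopsis also says "Pharmacokinetic parameters (clearance, mean residence time, volume of distribution, and terminal half-life) will be estimated by fitting noncompartmental analysis individually". It makes an exception for AUC, which it takes as only the part of the curve lying above the preceding trough. SAP 4.9.1.3 does not mention that rule.

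**The concern.** Dose divided by AUC0-inf equals clearance only when the whole area comes from that one dose. At infusion 5 it does not. The subject starts the profile with IgG left from at least seven earlier infusions, and extrapolation to infinity counts all of it. The denominator is too large, so CL is too small. Vz and Vss are too small by the same route if they are derived from this CL; the text reviewed gives no formula for either.

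The baseline correction does not help. It removes IgG present before any immunoglobulin therapy, which is endogenous IgG rather than carry-over.

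PK parameters of total IgG are a primary PK endpoint, and the synopsis names clearance and volume of distribution among them. A clearance near half its true value would misdescribe the product. If half-life in days is similar on both schedules, the error is also larger for 21-day than for 28-day subjects, which would produce a schedule difference that comes from the formula alone.

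**Working it through.** The documents give no CL, AUC or half-life value in days, so there is no figure of the plan's own to reproduce.

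**Inputs from the documents.** Dosing interval τ = 21 or 28 days, with a window of ±4 days. Four GC5107 infusions plus at least three IGIV infusions come before infusion 5, which is therefore at least the eighth consecutive dose. Infusion 5 is said to correspond to about five half-lives.

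**Assumptions.** Linear kinetics, one compartment, equal doses, infused (baseline-corrected) IgG. A half-life in days has to be assumed; 16.8 to 35 days is used.

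**Step 1: formula.** Let r = 2^(−τ/t½). At steady state AUC0-inf = (dose/CL)/(1 − r), so dose/AUC0-inf = CL × (1 − r), and the fold understatement is 1/(1 − r). If only eight doses are counted, it is (1 − r^8)/(1 − r).

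**Step 2: the documents' own half-life statement.** Four intervals have elapsed at infusion 5. If they equal five half-lives, t½ = 0.8τ, r = 2^(−1.25) = 0.420, and the factor is 1/0.580 = 1.73. If five intervals are meant, t½ = τ, r = 0.5, and the factor is 2.00. Counting eight doses gives 1.72 and 1.99.

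**Step 3: a common half-life in days (assumed).**

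| t½ (days) | 21-day: fold low | 28-day: fold low | Apparent CL, 21-day / 28-day |
|---|---|---|---|
| 16.8 | 1.73 | 1.46 | 0.85 |
| 21 | 2.00 | 1.66 | 0.83 |
| 28 | 2.47 | 2.00 | 0.81 |
| 35 | 2.94 | 2.35 | 0.80 |

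With eight doses only, the ranges are 1.72 to 2.83 (21-day) and 1.46 to 2.32 (28-day). The last column is the spurious schedule difference, 15 to 20%. Under step 2 the half-life scales with τ and there is no such difference.

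**Step 4: does the model matter?** In a two-compartment check (assumed fast half-life 2 days, 40% fraction), dose/AUC0-inf is 0.59 to 0.60 of true CL at t½ = 0.8τ and 0.51 to 0.52 at t½ = τ. Direction and rough size are unchanged.

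**Step 5: the replacement.** At steady state AUC0-τ = dose/CL, so dose/AUC0-τ returns CL exactly. With eight doses it is 1/(1 − r^8) of true CL: 1.001 at 0.8τ and 1.004 at τ. At 35 days it is 1.012 (28-day) and 1.037 (21-day).

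**Step 6: which τ?** Suppose infusion 6 is 4 days early or late and AUC runs over the actual interval. For t½ from 0.8τ to τ, dose/AUC is then 1.15 to 1.16 (early) or 0.89 to 0.90 (late) of true CL on the 21-day schedule, and 1.11 to 1.12 or 0.91 to 0.92 on the 28-day schedule. With the regular τ, and λz used to reach it, the ratio is 1.00. If instead the interval before infusion 5 was 4 days short or long, a residual of 0.93 to 1.07 (21-day) or 0.95 to 1.05 (28-day) remains.

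**Step 7: uncorrected values.** Assume a trough of 700 mg/dL, of which 100 or 300 mg/dL is endogenous, and t½ = τ. Infused IgG then falls from 2 × (700 − endogenous) to (700 − endogenous) over the interval, with mean (700 − endogenous)/ln 2, that is 866 or 577 mg/dL. Even dose/AUC0-τ is then 866/966 = 0.90 or 577/877 = 0.66 of true CL.

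**The case against.** The strongest counter-argument is that the direction depends on which AUC rule governs. The SAP presents itself as elaborating the protocol, and the synopsis takes AUC above the previous trough. On that rule the area over one interval is (dose/CL) × [1 − ln2 × (τ/t½) × r/(1 − r)], and dose divided by it overstates CL by 2.7-fold (t½ = 0.8τ) to 3.3-fold (t½ = τ). This is right as arithmetic and is a reason to reconcile the two documents. It does not rescue the SAP: section 4.9.1.3 states no trough subtraction, and the synopsis rule would replace one bias with another.

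Three further points have some force.
- The upper end of the range rests on an assumed half-life. The documents' own statement supports only 1.73 to 2.00, and the schedule difference needs a common half-life in days. Both are conditional.
- The text reviewed did not include protocol 7.3 and 9.1.6 or SAP 4.9.2, so a steady-state parameter defined there cannot be excluded. The explicit CL formula in 4.9.1.3 would still need correcting.
- AUC0-t may come close to the interval AUC if the last sample falls at the end of the interval. That eases the repair, but CL is tied to AUC0-inf.

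It is also true that the consequences are limited. Half-life from λz, Cmax, troughs and incremental recovery do not use this formula.

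**Conclusion.** The point holds. As written, SAP 4.9.1.3 understates CL for total IgG at any half-life, given linear kinetics and repeated equal doses. The size is 1.73- to 2.00-fold on the documents' five-half-lives remark, and 1.46- to 2.94-fold over an assumed 16.8 to 35 days. Uncorrected values carry a further downward bias from endogenous IgG, whose size depends on assumed levels. Confidence in the formula error and its direction is high; the exact factor is conditional.

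This should be fixed because clearance is part of a primary PK endpoint. It does not touch the primary efficacy or primary safety test.

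**What to change.** In SAP 4.9.1.3:
- Add AUC0-τ for total IgG, with τ the subject's regular interval (21 or 28 days) rather than the actual time to infusion 6. If the infusion-6 pre-dose sample is off schedule, interpolate log-linearly, or extrapolate with λz, to τ.
- Set CL = dose/AUC0-τ, Vz = CL/λz, MRT = [AUMC0-τ + τ × AUC(τ to infinity)]/AUC0-τ minus half the infusion duration, and Vss = CL × MRT. In the two-compartment check these return CL exactly and MRT and Vss to within 0.001.
- Keep AUC0-inf as a descriptive output only.
- Report CL on both uncorrected and baseline-corrected values, and say that the uncorrected value stays biased low by endogenous IgG.
- State that an off-schedule interval before infusion 5 leaves a small residual error, and list actual infusion dates.

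Then check the AUC definition against the protocol synopsis, protocol 7.3 and 9.1.6, and SAP 4.9.2, and record any departure from the protocol in SAP 4.11, which already serves that purpose.

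The cost is SAP wording and possibly one entry in 4.11. Total IgG is already drawn before every infusion, so the infusion-6 pre-dose sample closes, or nearly closes, the interval without extra sampling.
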